Cohort 1 will enroll subjects with malignant thyroid tumors with HRAS mutations, independently of thyroid histology. Any subject with a non-hematological HRAS mutant tumor who meets eligibility criteria may be enrolled in the first stage of Cohort 2. Subjects with HNSCC, salivary malignancies and urothelial carcinomas may be more frequently enrolled in Cohort 2 due to the relatively high rate of HRAS mutations in these indications; however, enrolment is not limited to these tumor types. Subjects with malignant thyroid tumors with HRAS mutations will only be enrolled in cohort 1. Based on the anti-tumor activity observed during stage 1 of cohort 2, the protocol was amended (Amendment 3) to restrict enrollment in stage 2 of Cohort 2 to subjects with HNSCC with HRAS mutations only.

Cohort 3 will enroll subjects (N=20 evaluable) who have SCC with HRAS mutations. The purpose of this cohort is to explore tipifarinib's anti-tumor activity in HRAS mutation positive SCCs independent of tissue origin.

Tipifarnib will be administered at a starting dose of 600 mg, po, bid daily on days 1-7 and 15-21 of 28-day treatment cycles. In the absence of unmanageable toxicities, subjects may continue to receive tipifarnib treatment for up to 12 months in the absence of disease progression and unmanageable toxicity. Treatment may continue beyond 12 months upon agreement of the Investigator and Sponsor.

Tumor assessments will be performed at screening and approximately every 8 weeks for the first 6 months (cycles 2, 4, 6) and then every 12 weeks (cycles 9, 12, 15, etc.) until disease

progression, starting at the end of Cycle 2. Additional tumor assessments may be conducted if deemed necessary by the Investigator or for a confirmation of an objective response. Subjects who discontinue tipifarnib treatment for reasons other than disease progression must continue tumor assessments until disease progression, withdrawal of subject's consent to study procedures or initiation of another anticancer therapy.

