Grade 2 Recurrent or Grade 3 Renal	Manage with BSC, including hydration and correction of electrolyte abnormalities, if appropriate. If not manageable, interrupt tipifarnib treatment until recovery to grade 1 or better	Upon recovery to ≤ grade 1, restart tipifarnib at the next lower dose level (see Table 2). If grade 2 or 3 renal toxicity recurs, upon recovery to ≤ grade 1, re-start tipifarnib at the next lower dose level (see Table 2).
Grade 2 non-tolerable Neurological	Manage with BSC. If not tolerable, interrupt tipifarnib treatment until recovery to grade 2 tolerable or better	Upon recovery to grade 2 tolerable or better, re-start tipifarnib at the next lower dose level (see Table 2).
		If grade 2 intolerable neurological toxicity recurs, upon recovery to grade 2 tolerable or better, re-start tipifarnib at the next lower dose level (see Table 2).
Grade 3 Neurological	Discontinue tipifarnib permanently	

In exceptional circumstances, dosing delays or skipping of dosing for reasons other than the management of toxicity will be allowed at the judgement of the investigator as long as 50% of the total dose is maintained in a given cycle.

Upon restarting tipifarnib following a treatment interruption, the cycle and dosing day are to be defined by the following:

- If a dose delay/interruption occurs and resolves within a cycle, dosing picks up where it left off
 - o For example, if a subject's treatment is held on Day 3, subject recovers 14 days later (nominal Day 17 in the cycle) and resumes tipifarnib treatment, the subject is considered to be dosing on Day 3 of the same cycle.
- If the delay goes beyond the cycle (> nominal day 28 of that cycle), upon recovery, the subject should be started at Day 1 of the next cycle.
 - o For example, if a subject's treatment is held on Day 3, subject recovers 30 days later (nominal Day 33 in the cycle) and resumes tipifarnib treatment, the subject is considered to be dosing on Day 1 of the next cycle.

Radiographic imaging for tumor response must maintain the fixed time schedule and is invariant to the drug exposure of the subject. Radiographic imaging will be performed at least once approximately every 8 weeks for 6 months, thereafter once approximately every 12 weeks. All other procedures/visits can follow the cycle's drug administration.

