11.4 Day 1 (+/- 2 days) of Cycle 2 and Beyond

The following procedures will be performed at this visit:

- Record subject weight and vital signs (blood pressure, pulse, temperature)
- ECOG performance status
- Physical examination
 - For subjects enrolled in France, physical examinations will include questioning about potential visual changes. If clinically indicated, a visual acuity test will be performed. If abnormal results are observed, subjects will be referred to an ophthalmological consultation. Additional physical examinations will be conducted as clinically indicated.
- Hematology
- Chemistry (fasting not required)
- Serum/urine pregnancy test for females of child-bearing potential only
- Concomitant medications
- Assessment of adverse events

In addition to the above procedures, the clinical site will conduct a drug accountability on the returned empty bottles and unused medications.

11.5 Day 22 (±5 days) of Cycles 2, 4, 6 and Cycles 9, 12, 15, etc.)

Tumor response assessment should occur approximately every 8 weeks for the first 6 months of a subject's participation; thereafter, tumor response assessment should occur approximately every 12 weeks until disease progression. The tumor response assessment schedule (every 8-12 weeks) should be maintained regardless of dosing delays or additional imaging assessments performed.

The following procedures will be performed at this visit:

- Tumor radiological assessments: CT scan with a contrast agent is the preferred imaging method and the same technique should be used at baseline and post-treatment assessments.
 - In subjects with HNSCC, CT scan coverage at screening should encompass scans
 of the neck (including the skull base), chest and abdomen (including the liver and
 adrenals). Any other areas of disease involvement should be scanned based on
 the subject's signs and symptoms.
 - o In subjects with other solid tumors, scan coverage should be appropriate to ensure that all areas of disease involvement are scanned.

o For the purposes of tumor assessment recording, the nomenclature Cycle 2 Day 22, Cycle 4 Day 22, Cycle 6 Day 22, Cycle 9 Day 22, Cycle 12 Day 22, etc. is used to name the tumor assessment visits. However, due to treatment delays or interruptions, it may happen that the tumor assessment visit will not coincide with the current treatment cycle for a given subject.

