12.2 Endpoints

12.2.1 Efficacy

The objective response rate will be estimated for each tumor histology type evaluated. The estimate of the objective response rate will be calculated based on the maximum likelihood estimator (i.e., crude proportion of subjects whose best overall response is Complete Response (CR) or PR. The estimate of the objective response rate will be accompanied by 2-sided 95% exact binomial confidence intervals.

The duration of objective response will be calculated for subjects who achieve CR or PR. For such subjects, the duration of objective response is defined as the number of days from the start date of PR or CR (whichever response is achieved first) to the first date that progressive disease is objectively documented. Disease progression will be determined by the Investigator using RECIST (version 1.1). The duration of objective response will be right-censored for subjects who achieve CR or PR and meet 1 of the following conditions: 1) non-protocol anticancer treatment started before documentation of disease progression, 2) death or documented disease progression after more than 1 missed disease assessment visit, or 3) alive and does not have documentation of disease progression before a data analysis cutoff date.

The duration of objective response will be summarized descriptively using the Kaplan-Meier method. The 50th percentile of the Kaplan-Meier distribution will be used to estimate the median response duration.

Progression free survival will be defined as the time (in months) from enrollment to either first observation of progressive disease or occurrence of death due to any cause within 126 days (approximately 2 time intervals for tumor assessments) of either first administration of tipifarnib or the last tumor assessment. In subjects without a progression date or with a death date more than 126 days after the first administration of study drugs or the last tumor assessment, the PFS time should be censored on the date of last tumor assessment or date of first administration of study tipifarnib. Progression free survival analyses should consider tumor assessments after treatment discontinuation or metastatic surgery. Sensitivity analyses for PFS will be performed according to the FDA Guidance for Industry Clinical Trial Endpoints for the Approval of Cancer Drugs and Biologics (May 2007).

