Tumor assessments will be performed at screening and approximately every 8 weeks starting at the end of cycle 2 for the first 6 months (Cycles 2, 4, 6) and then every 12 weeks (Cycles 9, 12, 15, etc.), or sooner if deemed necessary by the Investigator, and will continue until disease progression. A tumor assessment will be performed upon treatment discontinuation (End of Treatment visit) if the reason for discontinuation is other than disease progression and no tumor assessment was performed in the prior 8 weeks, or a tumor assessment is required for the confirmation of response to treatment. Subjects who discontinue treatment for reasons other than disease progression must continue tumor assessments until disease progression, withdrawal of subject's consent or initiation of another anticancer therapy. Determination of objective tumor response will be performed by the Investigator. However, tumor images may be de-identified of subject's personal information at the clinical sites and collected by the Sponsor or designee to undergo an external independent radiological review if the sponsor deems it necessary for the final assessment of the efficacy of the treatment. If an independent radiological review were to be conducted, reviewers would be blinded to Investigator's tumor response assessments. An independent review committee charter would be generated to provide the specific procedures that would be filed with Institutional Review Board (IRB) and regulatory authorities.

Subjects with a solitary site of disease who have experienced a response may be considered for surgical resection. Subjects with a Partial Response (PR) and residual disease after salvage surgery are eligible to continue on study therapy.

Upon disease progression, all subjects in the study cohort will be followed approximately every 12 weeks for survival and the use of subsequent therapy until either death or 12 months after accrual in the subject's study cohort has been completed, whichever occurs first. Information on survival and subsequent anticancer therapy may be collected by phone.

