4.6. Study Assessments

Details of scheduled assessments are displayed in Table 1 of the Protocol.

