9.2. Exploratory Efficacy Analyses

The duration of objective response (DOR) will be calculated for subjects who achieve CR or PR. For such subjects, the DOR is defined as the number of days from the start date of PR or CR (whichever response is achieved first) to the first date that progressive disease is objectively documented. Disease progression will be determined by the Investigator using RECIST (version 1.1). The DOR will be right-censored at the date for subjects who achieve CR or PR and meet 1 of the following conditions: 1) when non-protocol anticancer treatment started before documentation of disease progression, 2) when death prior to documented disease progression or documented disease progression after more than 1 missed disease assessment visit, or 3) when alive and does not have documentation of disease progression before a data analysis cutoff date. (Therefore, analysis cutoff date will be used as the censoring date).

Progression free survival (PFS) will be defined as the time (in months) from first dose (Cycle 1 Day 1) to either first observation of progressive disease or occurrence of death due to any cause within 126 days (approximately 2 time intervals for tumor assessments) of either first administration of tipifarnib or the last tumor assessment. Observation of progressive disease can be by either documented radiographic progression (i.e., scan results) or documentation of symptomatic or clinical progression agreed upon and documented by investigators. In subjects without a progression date or with a death date more than 126 days after the first administration of study drugs or the last tumor assessment, the PFS time should be censored on the date of last tumor assessment or date of first administration of study tipifarnib. PFS analyses should consider tumor assessments after treatment discontinuation or metastatic surgery.

The DOR and PFS, will be summarized descriptively using the Kaplan-Meier (KM) method. The 25th, 50th, and 75th percentiles of the Kaplan-Meier distribution will be used to describe the median response duration and median PFS.

The median DOR and PFS and corresponding pointwise 95% confidence interval will be displayed by cohort for the FAS population and for the PP population, and for the subgroups.

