The KM curves of DOR and PFS by each cohort will be displayed for the FAS population, the PP Population, and for the subgroups in figures. A per subject summary of DOR, such as treatment initiation date, progression date, first response date, durations, censoring status, best overall response, and analysis population inclusion, will be provided. Similarly, a per subject summary of PFS, including enrollment date, treatment initiation date, progression date, duration, censoring status, best overall response, and analysis population inclusion, will also be provided.

Subgroup analysis may be conducted to estimate PFS and DOR in the subset of subjects with partial response. Sensitivity analysis may be conducted to assess the impact of the median survival estimation method. Interpolation based estimates can be used to estimate the median

Protocol KO-TIP-001

survival whenever the sample size is small or there is not sufficient information (events) to robustly estimate the median survival based on KM function.

Further analysis may include the comparison of the PFS between tipifarnib and prior therapies. A *P* value comparing the two PFS profiles (prior therapy and the current using tipifarnib) will be obtained using Wei-Lin (Cox regression based) robust estimator.

If biomarkers including somatic mutations in archival tumor tissue have been successfully obtained for enough subjects, the relationship of the detection of tissue biomarkers potentially related to tipifarnib activity will be investigated as described in the protocol.

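### The 126-day PFS death limit equals about two scan intervals only while scans are 8 weeks apart, and protocol 10.1 and 11.6 depart from the imaging schedule

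*SAP*

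**What the plan says.** **PFS rule.** SAP 9.2 counts a death as a PFS event if it occurs "within 126 days (approximately 2 time intervals for tumor assessments") of first dose or the last scan. Protocol 12.2.1 has the same rule. Subjects "with a death date more than 126 days after the first administration of study drugs or the last tumor assessment" are censored at the last scan, or at first dose.

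**Scan schedule.** The protocol synopsis sets scans "approximately every 8 weeks for the first 6 months (cycles 2, 4, 6) and then every 12 weeks". Protocol 9.5 agrees: "Radiographic imaging will be performed at least once approximately every 8 weeks for 6 months, thereafter once approximately every 12 weeks". So does 11.5: "thereafter, tumor response assessment should occur approximately every 12 weeks until disease progression". SAP 4.1 repeats it: "and then every 12 weeks (Cycles 9, 12, 15, etc". Protocol 8.1 and Table 1 note 9 give the same schedule, and the note adds a window of ±5 days around Day 22. SAP 4.6 sends the analyst to that table: "Details of scheduled assessments are displayed in Table 1 of the Protocol".

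**Departures.** Protocol 10.1 keeps scans about 8 weeks apart after Cycle 2 until progression, with no change to 12 weeks. Protocol 11.6 waives the End of Treatment scan only if one was done in the preceding 4 weeks. Table 1 note 9, protocol 8.1 and 10.1, and SAP 4.1 all use 8 weeks.

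**Use of PFS.** PFS is exploratory and mainly descriptive, but SAP 9.2 also allows a P value "comparing the two PFS profiles (prior therapy and the current using tipifarnib").

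**The concern.** The plan gives its own reason for 126 days: about two assessment intervals. Once scans move to every 12 weeks, the number no longer meets that reason. The same history (one missed scan, then death without recorded progression) is always an event early in the trial and may be censored later. The subjects exposed are those who stay progression-free longest.

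At stake are the Kaplan-Meier curves and medians for PFS by cohort, population and subgroup, and the optional comparison with PFS on the last prior therapy. SAP 8.3 defines that earlier PFS with no death limit at all. The PFS sensitivity analyses in protocol 12.2.1 are specified by reference to an FDA guidance, and the protocol itself names no other limit.

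The conflict in 10.1 bears on this directly, because 126 days would fit throughout only if 10.1 governed. The conflict in 11.6 leaves a site unsure whether to scan a subject whose last scan is 4 to 8 weeks old.

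**Working it through.** **Inputs.** Limit of 126 days (SAP 9.2, protocol 12.2.1). Cycles of 28 days, with scans on Day 22 of Cycles 2, 4, 6, 9, 12 and so on, ±5 days (Table 1 note 9). Months = days/30.4375 (SAP 7.1). I read the limit as running from the last scan where there is one, and otherwise from first dose.

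**Scan days.** 28 × (n − 1) + 22 gives day 50 (C2), 106 (C4), 162 (C6), 246 (C9) and 330 (C12). The gaps are 56, 56, 84 and 84 days.

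**The plan's own figure.** 126/56 = 2.25, so about 2 is reproduced on 8-week scans: 2 × 56 = 112 days, plus 14.

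**By last scan:**

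| Last scan | Next two scans due after | 126 days in mean intervals | 126 minus second due day | Death after one missed scan, but censored |
|---|---|---|---|---|
| C2 (day 50) | 56 and 112 days | 126/56 = 2.25 | +14 | none |
| C4 (day 106) | 56 and 140 days | 126/70 = 1.8 | −14 | days 127-139 |
| C6 (day 162) or later | 84 and 168 days | 126/84 = 1.5 | −42 | days 127-167 |

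With no scan, the first two are due 49 and 105 days after first dose, so 126 days covers both.

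**Examples, each with one missed scan.**
- Last scan day 50, day-106 scan missed, death day 155: 155 − 50 = 105 days, an event.
- Last scan day 106, day-162 scan missed, death day 235: 235 − 106 = 129 days, censored at 106/30.4375 = 3.5 months rather than an event at 235/30.4375 = 7.7.
- Last scan day 162, day-246 scan missed, death day 300: 300 − 162 = 138 days, censored at 162/30.4375 = 5.3 months rather than an event at 300/30.4375 = 9.9.

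**Limits that follow the schedule.** Second scheduled scan plus the same 14 days: 112 + 14 = 126, 140 + 14 = 154, 168 + 14 = 182. With ±5 days at both ends, the second scan can fall up to 122, 150 or 178 days after the last one, so each limit leaves a 4-day margin.

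**Number of subjects (assumed inputs, not in the documents).** Of 30 HNSCC subjects, suppose 30-60% are progression-free at the Cycle 6 scan, and 5-10% of these die without recorded progression 85-167 days after their last scan, spread evenly over those days. The censored part is 41 of 83 days (49%).
- Low: 30 × 0.30 × 0.05 × 0.49 = 0.2.
- High: 30 × 0.60 × 0.10 × 0.49 = 0.9.

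The same rates over all 75 subjects multiply this by 2.5, giving 0.6 to 2.2. Deaths after a Cycle 4 last scan are not included.

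**Protocol 10.1.** Take progression as uniform over days 162-330. Scans 8 weeks apart fall on days 218, 274 and 330; scans 12 weeks apart fall on days 246 and 330. The mean shift in the recorded date is (56 × 28 − 28 × 28 + 28 × 56 + 0)/168 = 14 days later on 12-week scans.

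**Protocol 11.6.** If treatment stops without progression at a random point in the scan cycle, the last scan is 4-8 weeks old in (8 − 4)/8 = 50% of subjects on 8-week scans and (8 − 4)/12 = 33% on 12-week scans. For these subjects the two rules give different instructions.

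**The case against.** A fixed limit bounds unobserved time equally for everyone, which is a defensible choice. The examples above differ in unobserved time (105, 129 and 138 days) as well as in phase. The 126-day rule is prespecified and identical in both documents. The trial is open label, and SAP 4.0 (January 2021) postdates the two 2020 data cuts it names in 7.2, so replacing the main rule now would be hard to defend. This stands, and it is why the main rule should stay. It does not rescue the description, which is inaccurate once a 12-week gap is among the next two.

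A schedule-based limit is not perfect either. Protocol 11.7 allows scans every 8-12 weeks after treatment stops, and for a subject scanned every 8 weeks after Cycle 6, 182 days is 182/56 = 3.25 intervals. That also stands, and it is a further reason to confine the new limit to a sensitivity analysis.

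Protocol section 10 opens by pointing to Table 1, and SAP 4.6 does the same, so 10.1 and 11.6 are text conflicts that change no analysis rule. That is fair; they still give sites two instructions. Whether the guidance-based sensitivity analyses treat these deaths differently cannot be checked from the documents.

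**Conclusion.** The point holds as a minor one. The figure of 126 days is about two intervals with no scan or a Cycle 2 last scan, 1.8 after Cycle 4, and 1.5 from Cycle 6 on. Some deaths after a single missed scan are therefore censored against the plan's stated rationale. On the assumed inputs, about one HNSCC subject or fewer is affected; that range is only as good as those inputs. SAP 9.2 also accepts documented clinical progression as an event, which keeps the number small.

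Stronger readings that a reader might infer, and that the documents do not support:
- *The efficacy decision is affected.* It rests on ORR, which does not use this rule.
- *PFS is biased in a known direction.* Censoring removes both the event and the follow-up after the last scan, so the curve can move either way.
- *A far larger share of deaths is censored on 12-week scans than on 8-week scans.* Any such percentage contrast depends on the ranges compared. A range on 8-week scans that stops at day 126 must give 0%.
- *Duration of response is also undefined, because the schedule is unclear.* SAP 4.1 and 4.6 give the analyst the schedule for counting missed visits.
- *Protocol 11.7 is a third conflict.* Its 8-12 weeks is compatible with either schedule.

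**What to change.** 1. In SAP 9.2 and protocol 12.2.1, correct the parenthetical: 126 days is about two intervals when the next two scans are 8 weeks apart, and fewer from a Cycle 4 last scan on. Keep 126 days as the main rule.
2. In SAP 9.2, add a PFS sensitivity analysis with the death limit at the second scheduled assessment after the last scan plus 14 days: 126 days for no scan or a last scan before Cycle 4, 154 days for Cycle 4, and 182 days for Cycle 6 or later. With no scan the strict formula gives 105 + 14 = 119 days; keep 126 so that the sensitivity rule is never tighter than the main one. List the addition in SAP 14.
3. Change protocol 10.1 to every 8 weeks for 6 months and then every 12 weeks.
4. Change the look-back in protocol 11.6 from 4 to 8 weeks, and state whether it counts back from the visit or from the last dose, which are about 30 days apart.

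The cost is one condition in the PFS derivation, one extra run, and wording. No visit or procedure is added. SAP section 2 requires changes to be on file before the database is frozen.

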6.2 Secondary Objectives and Endpoints

Secondary Objective: Safety and tolerability of tipifarnib in subjects with locally advanced unresectable or metastatic, relapsed and/or refractory, HRAS mutant non hematological malignancies.

Secondary Endpoint: Treatment-emergent adverse events (TEAE) and SAEs evaluated according to NCI CTCAE v.4.03.

Exploratory Objective and Endpoints

Exploratory Objective 1: To determine the antitumor activity in terms of PFS and DOR of tipifarnib in subjects with locally advanced unresectable or metastatic, relapsed and/or refractory, HRAS mutant non hematological malignancies.

Exploratory Endpoints 1: PFS and DOR according to RECIST 1.1.

Exploratory Objective 2: To explore the feasibility of collecting archival biopsies and analyzing these biopsies for the detection of tissue biomarkers potentially related to tipifarnib activity.

Exploratory Endpoints 2: Molecular analyses of archival tissue samples.

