3.3. Exploratory Objective and Endpoints

Exploratory Objective 1: To determine the antitumor activity in terms of progression free survival (PFS), and duration of response (DOR) of tipifarnib in subjects with locally advanced

Protocol KO-TIP-001

unresectable or metastatic, relapsed and/or refractory, HRAS mutant non hematological malignancies.

Exploratory Endpoints 1: PFS, and DOR according to RECIST 1.1.

Exploratory Objective 2: To explore the feasibility of collecting archival biopsies and analyzing these biopsies for the detection of tissue biomarkers potentially related to tipifarnib activity.

Exploratory Endpoints 2: Molecular analyses of archival tissue samples.

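### SAP 9.2 counts clinical progression as a PFS event but not as a DOR event, although both endpoints are stated per RECIST 1.1 and the change is not listed in Section 14

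*SAP*

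**What the plan says.** The endpoint statements agree with each other. Protocol 6.2 has "Exploratory Endpoints 1: PFS and DOR according to RECIST 1.1" and SAP 3.3 has "Exploratory Endpoints 1: PFS, and DOR according to RECIST 1.1".

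SAP 9.2 then defines the two endpoints differently:

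- **DOR** runs from first response "to the first date that progressive disease is objectively documented", with progression judged by the investigator under RECIST 1.1. It is censored "when non-protocol anticancer treatment started before documentation of disease progression"; at death before documented progression, or at progression found after more than one missed assessment; and "when alive and does not have documentation of disease progression before a data analysis cutoff date". A closing parenthesis gives the analysis cutoff as the censoring date.
- **PFS** runs from first dose to progression, or to death within a 126-day window. Progression may be radiographic or may rest on "documentation of symptomatic or clinical progression agreed upon and documented by investigators". Subjects without an event are censored at the last tumor assessment or, failing that, at first dose.

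The PFS definition in Protocol 12.2.1 refers to the first observation of progressive disease and has no clinical or symptomatic clause. SAP Section 14, which records departures from the protocol, lists the addition of overall survival and a PFS/DOR sensitivity analysis on a subset of subjects. It does not list the clinical-progression clause.

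**The concern.** The PFS that SAP 9.2 would produce is not the PFS that both documents name as the endpoint. One responder can also carry two progression dates in the same report: one that ends PFS, and a later one, or none, for DOR. A reader who sets the two Kaplan-Meier summaries side by side would assume a common definition of progression.

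The clause also makes PFS depend partly on a clinical judgement in an open-label, single-arm study. PFS feeds the optional comparison with prior-therapy PFS in SAP 9.2, which yields a P value, so its event definition has some inferential use. No analysis stated in the SAP would show how much the clause matters. The options in 9.2 concern the subset with partial response and the method of estimating the median.

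**Working it through.** The documents give no figure to reproduce, so the check is a comparison of rules followed by an illustration.

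**Step 1: one subject, two endpoints.** Take a responder whose investigator documents clinical progression with no RECIST progression at that time. Under SAP 9.2, PFS is an event on that date. What happens to DOR depends on what comes next:

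| What happens next | DOR under SAP 9.2 |
|---|---|
| RECIST progression on a later scan | Event at the later date (censored if more than one visit was missed) |
| New anticancer therapy first | Censored, condition 1; date not clearly stated |
| Death first | Censored, condition 2; date not clearly stated |
| Alive, none of these | Censored at the analysis cutoff, condition 3 |

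In no row does DOR end with an event on the date on which PFS does.

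**Step 2: can a lenient reading close the gap?** Suppose documentation of progression in condition 3 includes clinical documentation. The subject in the last row is then no longer censored under condition 3, but is still not an event, because the event requires RECIST progression. The outcome would be undefined, and two programmers could resolve it differently.

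**Step 3: would later scans close it?** Not reliably. Protocol 11.7 requires follow-up visits only for subjects who stopped treatment for reasons other than death or progression, and 11.7.1 plans survival and therapy follow-up after progression. If a site records the clinical call as progression, no further scan is clearly required.

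**Step 4: illustration of direction.** All inputs here are assumed and none is in the documents. Let the time from response to first progression of any kind be exponential with median 8.0 months, so λ = ln 2 / 8 = 0.0866 per month. Let a share c of first progressions be clinical-only, with no later RECIST event.

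- Clinical progression counted as an event: median = 8.0.
- (a) Censored at clinical progression: median = ln 2 / ((1 − c)λ) = 8/(1 − c).
- (b) Carried event-free to a cutoff beyond the median: median = −ln(1 − 0.5/(1 − c))/λ.

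At c = 20%, (a) gives 8/0.8 = 10.0 months and (b) gives −ln(0.375)/0.0866 = 11.3 months.

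| c | (a) censored, months | (b) carried to cutoff, months |
|---|---|---|
| 10% | 8.9 | 9.4 |
| 20% | 10.0 | 11.3 |
| 30% | 11.4 | 14.5 |
| 40% | 13.3 | 20.7 |

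The step from 8.0 to (a) is the effect of leaving clinical progression out of DOR. The step from (a) to (b) belongs to the cutoff-date censoring rule. Model (a) treats the censoring as non-informative, which is doubtful when it follows clinical worsening.

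**Step 5: weight of one subject.** If the 30% design alternative held in the 30 planned HNSCC subjects, there would be 0.30 × 30 = 9 responders, and one discordant subject would be 1/9 = 11% of the DOR sample.

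**The case against.** The best defence has four parts.

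First, PFS and DOR are exploratory and summarised descriptively, and the primary analysis is untouched. That stands, and it limits the weight of the point.

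Second, the endpoints differ by design anyway: death within the window is a PFS event but is censored for DOR. That is true, but it is an open difference in what is measured. Here the single word progression has two meanings.

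Third, there are safeguards. Protocol 12.2.1 promises PFS sensitivity analyses under a regulatory guidance, and the SAP does not withdraw them. The per-subject PFS and DOR summaries in SAP 9.2 would make a discordant subject visible. Subjects who stop for reasons other than progression keep being scanned. This stands only in part. SAP 9.2 does not carry the promised analyses over, a listing shows a conflict without resolving it, and the scan rules differ: Protocol 8.1 ends scans at new anticancer therapy, while 11.7 continues them.

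Fourth, the effect on DOR may be small. A reader might build a case with response at month 2, clinical progression at month 6 and a cutoff at month 20, and read DOR as 20 − 2 = 18 months instead of 6 − 2 = 4. The documents do not support that as the size of the problem. It sets a censoring time against an event time. It needs 14 months with no RECIST progression, new therapy or death. Most of the gap comes from the cutoff-date rule, which applies to any responder alive without documented progression. This objection stands in full.

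**Conclusion.** The inconsistency is in the text and needs no assumption. PFS as programmed from SAP 9.2 would depart from the stated RECIST 1.1 endpoint, DOR would not, and Section 14 does not record the departure. A responder with clinical-only progression is a PFS event and not a DOR event.

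The size cannot be given, because the documents do not say how many responders progress clinically without RECIST progression. The medians under the working show direction under assumed inputs only.

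Three stronger readings are not supported:

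- That the primary result is affected. ORR, the two-stage rule and the sample size do not use this definition.
- That DOR is wrong by its own definition. RECIST-only DOR is the stated endpoint. The faults are the mismatch with PFS and censoring that is likely to be informative.
- That the clause was added after the data were seen. SAP version 4.0 is dated 05 January 2021 and names 2020 data cuts, but the documents do not show when the clause entered.

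The plan should be corrected, as a matter of moderate weight.

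**What to change.** In SAP 9.2:

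1. Define progression once for both endpoints, as RECIST 1.1 progression, with death added for PFS. Use this for the main analysis.
2. In that analysis, censor subjects with clinical progression but no RECIST progression at their last tumor assessment for both PFS and DOR, so that DOR does not run on to the cutoff. State that a death within the 126-day window remains a PFS event.
3. Add one sensitivity analysis in which clinical progression is an event in both PFS and DOR. This analysis, and not the RECIST-only main analysis, shows how far DOR is lengthened by leaving clinical progression out. In the illustration at c = 20%, the pair would read about 10.0 and 8.0 months.
4. List the change in Section 14.

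The cost is a few sentences and one extra table. No new data are needed, since SAP 9.2 already expects clinical progression to be documented. Main PFS may come out slightly longer, and the sensitivity table shows by how much.
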